2.3.4. Phase 1b 105RC101 Study Results

All eighteen planned patients have been treated in the phase 1 portion of this study as of the time of this protocol amendment (3 at 8 mg/kg and 15 at 10 mg/kg).

2.3.4.1. Phase 1b 105RC101 Safety

Patients experienced expected TRC105 related adverse events of grade 2 infusion reaction and grade 1 epistaxis, gingival bleeding, headache, rash, and fatigue; and expected axitinib adverse events of grade 1-3 hypertension, grade 1 hand-foot syndrome and grade 1 proteinuria. Two patients dosed with TRC105 at 8 mg/kg with axitinib developed grade 2 creatinine elevations that reversed with hydration. Adverse events characteristic of each drug were not increased in

frequency or severity when both drugs were administered concurrently. Patients in the Phase 1b portion of the trial initially received axitinib at 5 mg p.o. BID and inpatient dose escalation of axitinib was performed to 7 mg p.o. BID and 10 mg p.o. BID, without the development of dose limiting toxicity. Ongoing patients have received TRC105 and axitinib for up to 12 months of treatment.

2.3.4.2. Phase 1b 105RC101 Efficacy

Eleven of 17 evaluable VEGFR TKI refractory patients demonstrated decreases in tumor burden ranging from 1.2% to 50% (including five partial responses per RECIST 1.1, four of which were in the fourth line setting).

2.3.5. Population to be Studied

Patients with histologically confirmed advanced clear cell RCC will be enrolled in the phase 2 portion of this trial. All histologies are eligible for participation in the Phase 1b portion.

2.3.6. Potential Risks and Benefits to Human Patients

2.3.6.1. Potential Risks

TRC105

Grade 3 anemia has occurred with TRC105 therapy at the recommended phase 2 dose. All patients treated with TRC105 should be monitored closely for anemia and treated appropriately, including the possibility of TRC105 dose reductions. Anemia may be caused by correctable mineral or vitamin deficiency. The anemia related to TRC105 is hypoproliferative in nature and is reversible with interruption of treatment, transfusion, erythropoietin, and other interventions as appropriate.

Gastrointestinal hemorrhage has occurred with TRC105 therapy. Patients with active ulcer disease or risk factors for ulcer disease are excluded from this study.

Grade 1 and 2 cutaneous telangiectasia related to TRC105 occur early in the course of therapy and have been the source of gingival bleeding and epistaxis. Telangiectasia are also seen in patients with hereditary hemorrhagic telangiectasia (HHT), a disease of CD105 haplotype insufficiency. Patients with HHT are at risk of hemorrhage from abnormal blood vessels and this could be exacerbated by treatment with TRC105. Other contraindications to TRC105 therapy include a history of significant hemorrhage or tumors located in the central chest or another location where bleeding is associated with high morbidity. All patients treated with TRC105 should be monitored for signs of hemorrhage and the risks and benefits of drug treatment reevaluated in any patient with hemorrhage.

Premedication including the use of glucocorticoid is required prior to infusion of TRC105 to reduce the frequency and severity of infusion reactions. Infusion reactions following TRC105 dosing generally occur with the first TRC105 dose and include a grade 4 vasovagal reaction that resolved without sequelae. Signs and symptoms of TRC105 infusion reactions include hypertension, hypotension, dyspnea, bronchospasm, chills/rigors, chills, sweats, fever, nausea, tachycardia, bradycardia, EKG changes, flushing, urticaria, pruritus, and headache, generally of

grade 1 and 2 severity. Potential infusion reactions seen with other therapeutic antibodies include angioedema, asthenia, throat irritation, rhinitis, vomiting, joint pain, fatigue and neurologic disorders including inflammation of the spine and/or brain.

Hypersensitivity reactions with infusions are a potential risk for sensitized patients, and TRC105 should be used with caution in patients with known hypersensitivity to any component of the drug product. Host anti-TRC105 antibodies to the murine or human portions of CHO-produced TRC105 are rare. In general, the risk of immunogenicity to therapeutic chimeric antibodies is small (<10%) and the clinical significance of immunogenicity is not well defined. The current trial will collect serial blood samples for anti-product antibody concentrations to further characterize the immunogenicity of TRC105 and potential clinical implications.

Grade 3 cerebrovascular hemorrhage resulting in hemiparesis occurred in one patient with hepatocellular cancer who was thrombocytopenic (who entered the study with a platelet count of 60,000/uL) in a study of TRC105 with sorafenib. Patients must have a platelet count of > 100,000/uL to enter this study (see inclusion criteria). A grade 2 transient ischemic attack was reported in a study of TRC105 and pazopanib. Grade 3 pancreatitis was also observed in this study. Transient Grade 3 hepatic encephalopathy occurred in one patient with cirrhosis and hepatocellular carcinoma who received TRC105 in combination with sorafenib. Additionally, Grade 5 intracranial hemorrhage occurred in one glioblastoma patient with markedly abnormal blood clotting parameters in a study of TRC105 with bevacizumab. A patient with glioblastoma developed temporary confusion and slurred speech following treatment with TRC105 and bevacizumab that required hospitalization for observation. Another patient with glioblastoma, who underwent resection and had a history of an abnormal collection of cerebral spinal fluid, developed a grade 2 cerebral spinal fluid leak. A third patient with glioblastoma and history of recurrent meningitis developed recurrent grade 3 bacterial meningitis while treated with bevacizumab and TRC105.

Grade 3 myocardial infarction (non-Q wave infarct associated with hypertension following an infusion reaction) was observed in a patient with hepatocellular cancer following treatment with TRC105 that resolved without sequelae. Patients with evidence of active coronary artery disease are excluded from participation in this trial (see exclusion criteria).

Adult respiratory distress syndrome that required temporary intubation occurred in one patient who received TRC150 with pazopanib, from which the patient recovered. Of note, interstitial lung disease has been added as an adverse drug reaction and warning/precaution to the core safety information for pazopanib. Pneumothorax (collapsed lung) has been observed in trials of TRC105 administered with a VEGFR TKI in patients with lung metastases.

A patient with renal cell carcinoma treated with TRC105 and axitinib developed grade 3 localized perforation of the large intestine at the site of an intraabdominal tumor metastasis that required percutaneous drainage and diverting colostomy.

Infections have been observed rarely. Grade 3 infected lipoma/cyst was observed in a Phase 2 study of TRC105 as a single agent in patients with metastatic bladder cancer. Grade 3 orbital cellulitis and grade 3 brain abscess were observed in patients treated with TRC105 and bevacizumab and considered possibly related to TRC105. Grade 1 and 2 gingivitis including

infection and ulceration has also been observed. Overall, infections have been observed in fewer than 5% of patients and have largely been considered unrelated to treatment with TRC105.

Reversible grade 3 colitis was reported in a patient treated with TRC105 and pazopanib

Grade 1-3 headaches have been observed following TRC105 treatment, generally within hours following completion of the initial infusion. Headaches are throbbing in nature, are not associated with radiographic abnormalities, and have responded to treatment with non-steroidal anti-inflammatory agents and to triptans. Headaches were particularly common when TRC105 and bevacizumab were initially dosed on the same day and were ameliorated when TRC105 was dosed one week following bevacizumab dosing and given over two days during the initial week of dosing.

Nasal congestion and periorbital edema have been observed with TRC105 dosing, particularly when dosed in combination with bevacizumab. The edema has been transient in nature and treated with corticosteroids.

Fatigue of grade 1- 3 severity has been reported following dosing with TRC105. Maculopapular rash and skin flushing of grade 1 and grade 2 severity have also been reported. A patient receiving treatment with TRC105 and sorafenib developed self-limited pancreatitis of grade 2 severity.

Axitinib

The most common ($\geq 20\%$) adverse reactions associated with axitinib use are diarrhea, hypertension, fatigue, decreased appetite, nausea, dysphonia, palmar-plantar erythrodysesthesia (hand-foot) syndrome, weight decreased, vomiting, asthenia, and constipation. Other rare but significant adverse events include hypertension and hypertensive crisis, hemorrhage, arterial and venous thromboembolism, reversible posterior leukoencephalopathy syndrome (RPLS), thyroid dysfunction, liver function abnormalities, proteinuria and gastrointestinal perforation or fistula. Further details are available in the package insert ([Section 20.3](#)).

Computed Tomography (CT) Scans

Patients will be exposed to a small amount of radiation as a result of the CT scans required in this study. This degree of exposure has not been associated with harmful health effects. In addition, the frequency of CT scans performed in this study is similar to the standard of care frequency. Patients with a medical contraindication to CT scans or known Iodinated contrast allergies may undergo MRI. There is minimal risk of MRI imaging in patients able to undergo this type of exam including very rare reports of gadolinium-induce nephrogenic systemic fibrosis in patients with poor renal function.

Magnetic Resonance Imaging (MRI):

MRI is a noninvasive imaging test used to diagnose and evaluate medical conditions. MRI does not use radiation and there are no known harmful side-effects. However, MRI may cause anxiety for people due to the loud banging made by the machine and the confined space of the testing

area. People with pacemakers, aneurysm clips, artificial heart valves, ear implants, or metal implants or foreign objects in their body are not permitted to have an MRI.

Bone Scans:

A bone scan is a test that can find cancer that has spread to the bones. A bone scan can often find a problem days to months earlier than a regular X-ray test. During a bone scan, a radioactive substance called a tracer is injected into a vein in your arm. The tracer travels through your bloodstream and into your bones. Then a special camera takes pictures of the tracer in your bones. A bone scan poses no greater risk than do conventional X-ray procedures. The tracers used in a bone scan produce very little radiation exposure — less than half that of a CT scan.

Venipuncture

Patients could also experience side effects from venipuncture for tests that will be done as part of this study including pain, tenderness or bruising at the site of collection, and rarely infection may occur at the spot where the needle is inserted.

Other Risks

This study treatment may involve risks to unborn children therefore patients should not become pregnant or father a baby while participating in this study. Patients should not nurse while on this study. Women of childbearing potential must have a negative pregnancy test before taking part in this study. Woman must be of non-child bearing potential due to surgical sterilization (at least 6 weeks following surgical bilateral oophorectomy with or without hysterectomy or tubal ligation) confirmed by medical history or menopause; or must agree to use two acceptable methods of birth control, one of which must be highly effective (see below), at the same time during study treatment (including during temporary breaks from treatment), and for at least 180 days after stopping TRC105 or axitinib. Men with pregnant partners and men with non-pregnant partners that are of childbearing potential must agree to use a condom with spermicide), during study treatment (including during temporary breaks from treatment), and for at least 180 days after stopping TRC105 or axitinib. The long term risk of infertility is unknown. Ovarian failure has been observed with other antiangiogenic agents.

Acceptable birth control methods considered highly effective:

- bilateral tubal ligation
- intrauterine device (IUD)
- vasectomy that has received medical assessment of surgical success
- Sexual abstinence*

* In the context of this protocol, sexual abstinence is considered a highly effective method of birth control only if refraining from heterosexual intercourse during the entire period of risk (i.e., during study treatment, including during temporary breaks from treatment, and for at least 180 days after stopping TRC105 or axitinib). If sexual abstinence is the highly effective method of birth control used, a second acceptable method is not required.

Acceptable birth control methods **not** considered highly effective:

- male or female condom with spermicide*
- cap, diaphragm or sponge with spermicide

* A female condom and a male condom should not be used together as friction between the two can result in either product failing.

2.3.6.2. Potential Benefits

TRC105 is an investigational product, and its efficacy has not been established. It is possible that the administration of TRC105 may result in clinical benefit (i.e., tumor response or prolonged stable disease).

2.3.7. Justification of the Dose, Schedule and Route of Administration of TRC105

The dose and schedule of TRC105 (8 mg/kg weekly up to 10 mg/kg weekly, 15 mg/kg every 2 weeks, and 20 mg/kg every 2 weeks) were selected based on safety, pharmacokinetics and early evidence of activity in the phase 1 study of TRC105 for patients with solid tumors (Study 105ST101) and in the Phase 1b study of TRC105 with bevacizumab. In phase 1, a weekly dose of 10 mg/kg and a dose of 15 mg/kg every two weeks were well tolerated and associated with clinical activity. Dose reduction was possible for treatment of anemia. In total, 15 patients have been treated at 15 mg/kg administered every two weeks and 4 patients have been treated at 20 mg/kg administered every two weeks; both doses were well tolerated. Doses of 8 and 10 mg/kg TRC105 weekly were tolerated in combination with bevacizumab, pazopanib and axitinib (in cohorts 1 and 2 of this study) and doses of TRC105 of 15 mg/kg every 2 weeks were tolerated in combination with sorafenib. Notably, while the initial schedule of TRC105 was adjusted to decrease the frequency of headaches, there was no potentiation of life threatening toxicities associated with bevacizumab, nor potentiation of common VEGF inhibitor toxicities (e.g., hypertension and proteinuria).

Given the limited experience dosing TRC105 with VEGF inhibitors, it is possible that TRC105 toxicities will potentiate axitinib toxicities, and vice versa. Therefore a TRC105 starting dose of 8 mg/kg weekly, which is 20% lower than the single-agent TRC105 MTD identified in the phase 1 single agent study and phase 1b study with bevacizumab, was selected. In addition a 6 mg/kg (-1) dose level has also been included and will be enrolled should 8 mg/kg of TRC105 in combination with axitinib exceed the MTD. As an added precaution, the first dose of TRC105 will be split and administered over 2 days (cycle 1 day 1 and cycle 1 day 4).

2.3.8. Conduct

The 105RC101 clinical trial will be conducted in compliance with the protocol, GCP, and the applicable regulatory requirements.

3. TRIAL OBJECTIVES AND PURPOSE

3.1. Purpose

The purpose of this study is to evaluate the safety and effectiveness of TRC105 in combination with axitinib.

3.1.1. Phase 1b Trial Objectives

3.1.1.1. Primary objectives

- To evaluate safety and tolerability and determine a recommended phase 2 dose for TRC105 when added to standard dose axitinib in patients with advanced renal cell carcinoma

3.1.1.2. Secondary objectives

- To look for preliminary evidence of improved antitumor activity when TRC105 is added to axitinib, by assessing overall response rate and progression-free survival
- To characterize the pharmacokinetic profile of TRC105 when given with axitinib
- To evaluate TRC105 immunogenicity by measuring Anti-Product Antibody (APA) formation
- To explore the pharmacodynamic changes in circulating angiogenic biomarkers involved in angiogenesis associated following treatment with TRC105 and axitinib

3.1.2. Phase 2 Trial Objectives

3.1.2.1. Primary Objective:

- To estimate the PFS of patients with advanced or metastatic RCC by RECIST 1.1 criteria in patients treated with axitinib and TRC105 compared to those treated with axitinib alone, following failure of one prior VEGF inhibitor.

3.1.2.2. Secondary Objectives:

- To estimate overall response rate by RECIST 1.1 and Choi criteria, including duration of response by RECIST 1.1
- To estimate the disease control rate (CR + PR + SD) at 16 weeks by RECIST 1.1 and Choi criteria
- To determine the frequency and severity of adverse events as assessed by NCI CTCAE (Version 4.0)
- To evaluate TRC105 immunogenicity as measured by Anti-Product Antibody (APA) concentrations
- To explore the effects of TRC105 on circulating angiogenic protein biomarkers

- To characterize the pharmacokinetic profile of TRC105 and axitinib

4. INVESTIGATIONAL PLAN

4.1. Overall Study Design and Plan

4.1.1. Overview

All patients must sign a consent form prior to undertaking any study-related procedures. Prospective patients will be screened to determine if they qualify for the study within 28 days of enrollment. Toxicities will be graded according to the NCI CTCAE Version 4.0.

4.1.1.1. Phase 1b Overview

This is a multicenter, open-label, nonrandomized, phase 1b, dose-finding study of TRC105 in combination with standard dose axitinib in patients with advanced RCC. Escalating doses of i.v. TRC105 will be administered weekly beginning with Dose Level 1 in combination with oral axitinib given as 5 mg p.o. BID daily. Intermediate dose TRC105 (below the MTD established during the trial) may be explored based upon clinical, PK, and/or biomarker data.

Weekly Dosing:

Dosing will begin at 8 mg/kg (cohort 1) however a -1 cohort has also been included (6 mg/kg) and will be enrolled if 8 mg/kg TRC105 plus axitinib exceeds the MTD. The first weekly TRC105 dose will be split into two doses whereby 3 mg/kg is administered on cycle 1 day 1 and the balance is administered on cycle 1 day 4. The entire weekly dose of TRC105 (6, 8 or 10 mg/kg) is then given on cycle 1 day 8 and weekly thereafter in combination with oral axitinib given as 5 mg p.o. BID. Those who tolerate TRC105 without any infusion reactions may be eligible for reduced infusion durations and decreased premedication (see [Section 6.1.6](#)).

Every Two Week Dosing:

In cohort 3 (10 mg/kg weekly during cycle 1; 15 mg/kg every two weeks beginning with cycle 2 day 1) and cohort 4 (10 mg/kg weekly during cycle 1; 20 mg/kg every two weeks beginning with cycle 2 day 1) the first weekly TRC105 dose will also be split into two doses whereby 3 mg/kg is administered on cycle 1 day 1 and the balance is administered on cycle 1 day 4. Starting on cycle 2 day 1 and beyond, TRC105 will be administered every two weeks on days 1 and 15.

After 2 cycles of treatment, patients who demonstrate a response of complete response (CR), partial response (PR) or stable disease (SD) will be eligible for additional treatment until progression.

Patients who exit the study for reasons other than drug-related dose-limiting toxicity prior to completion of the first 28-day cycle will be replaced. Inpatient dose escalation of TRC105 is not allowed.

Table 5: Dose Levels

Cohort	Number of Evaluable Subjects	Axitinib mg p.o., BID days 1-28	TRC105 mg/kg IV
-1	3-6	5	6 ^a

Cohort	Number of Evaluable Subjects	Axitinib mg p.o., BID days 1-28	TRC105 mg/kg IV
1 (Starting Dose)	3-6	5	8 ^a
2	3-6	5	10 ^a
Expanded Cohort 1	9-12 (up to 15 total at the MTD)	5	10 ^a
3	3-6	5	
 • 10 mg/kg weekly during cycle 1^b • 15 mg/kg every two weeks beginning with cycle 2 day 1^b
4	3-6	5	
 • 10 mg/kg weekly during cycle 1^b • 20 mg/kg every two weeks beginning with cycle 2 day 1^b
Expanded Cohort 2	At least 6 patients will be treated at the MTD (either cohort 3 or cohort 4 dose level)	5	
 • 10 mg/kg weekly during cycle 1^b • Either 15 or 20 mg/kg every two weeks beginning cycle 2 day 1^b

^a In cohort -1, 1, 2 and Expanded Cohort 1 TRC105 will be given weekly.

^b In cohorts 3 and 4 and Expanded Cohort 2, axitinib dosing will begin on cycle 1 day 1 and twice daily thereafter, and TRC105 will be administered weekly during cycle 1. The first weekly TRC105 dose will be split into two doses whereby 3 mg/kg is administered on cycle 1 day 1 and the balance is administered on cycle 1 day 4. Starting on cycle 2 day 1 and beyond, TRC105 will be administered every two weeks on days 1 and 15.

For cohorts 1 and 2, the DLT evaluation period, for purposes of dose expansion, will be the first 28 days of dosing axitinib and TRC105 together (e.g., from cycle 1 day 1 through cycle 1 day 28). Cycles are 28 days in duration.

For cohorts 3 and 4, the DLT evaluation will be the first 28 days of dosing axitinib with TRC105 every 2 weeks (e.g., from cycle 2 day 1 through cycle 2 day 28). Cycles are 28 days in duration.

Three patients will be initially enrolled and treated at each dose level. If none of these 3 patients experiences a dose-limiting toxicity (DLT) during the 28-day evaluation period, dose escalation will proceed following review of safety data with appropriate site staff including the principal investigators at all sites.

If 1 of 3 patients experiences DLT, the dose level will be expanded to 6 patients. The maximum tolerated dose (MTD) will have been exceeded if $\geq 33\%$ of patients experience DLT at a given dose level. DLT will have occurred when a patient has 1 or more toxicity listed in the table below that is at least possibly related to the combination of axitinib and TRC105 during the 28 day DLT evaluation period. Patients who exit the study for reasons other than DLT or any TRC105 dose delay > 2 days in cycle 2 (phase 1b cohort 3 and 4 only) prior to completion of the 28-day DLT evaluation period will be replaced to ensure an adequate safety assessment in each cohort. Patients who experience DLT and those without DLT who receive less than the prescribed dose of TRC105 or axitinib due to documented toxicity in Cycle 1 (for cohorts -1, 1, and 2) and in Cycle 2 (for cohorts 3 and 4) will be considered evaluable for dose escalation purposes. Upon agreement of the study investigators, a given TRC105 dose level may be reenrolled at $\geq 60\%$ of the axitinib dose intensity and/or the first dose of TRC105 may be delayed by one week (i.e., delayed to cycle 1 day 8).

Table 6: Dose Limiting Toxicity Definition and Criteria

Toxicity Category	Drug-Related Toxicity/Grade
Hematologic	Grade 4 neutropenia for ≥ 5 days
	Febrile neutropenia: grade 4 neutropenia with fever > 38.5 °C both sustained over a 24 hour period.
	Neutropenic infection: grade ≥ 3 neutropenia with grade ≥ 3 infection
	Anemia \geq grade 3
	Grade > 4 thrombocytopenia or grade ≥ 3 thrombocytopenia and grade ≥ 3 hemorrhage
Nonhematologic	Grade 3 or 4 nonhematologic toxicity with the following exceptions: 
 • Nausea, vomiting or diarrhea for < 48 hours^a • Asymptomatic electrolyte abnormalities that are corrected to grade 1 or better in < 48 hours^b

^aPatients with related grade 3 or 4 diarrhea, nausea or vomiting for ≥ 48 hours despite optimal medical therapy will require a one-level dose-reduction of TRC105.

^bPatients with related grade 3 or 4 electrolyte abnormalities that persist for ≥ 48 hours will require a one-level dose-reduction of TRC105.

Up to 15 patients with advanced renal cell carcinoma will be treated at the weekly dosing MTD (or top cohort if a MTD is not determined) to further characterize safety and tolerability. At least 6 patients with advanced renal cell carcinoma will be treated at the every two week dosing MTD (or top cohort if a MTD is not determined).

The recommended phase 2 dose for the combination will be determined by the study investigators, medical monitor, and TRACON after reviewing the toxicity and pharmacokinetic profile of the study combination.

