8.2.2. Serious Adverse Events

An adverse event that meets one or more of the following criteria/outcomes is classified as serious:

- Results in death
- Is life-threatening (i.e., at immediate risk of death)
- Requires in patient hospitalization or prolongation of existing hospitalization
- Results in persistent or significant disability/incapacity
- Results in congenital anomaly/birth defect
- Other important medical events that may not result in death, be life-threatening, or require hospitalization may be considered serious when, based upon appropriate medical judgment, they may jeopardize the patient or may require medical or surgical intervention to prevent one of the outcomes listed above. Examples of such events are intensive treatment in an emergency room for allergic bronchospasm; blood dyscrasias or convulsions that do not result in hospitalization; or the development of drug dependence or drug abuse.
- Cases of potential drug-induced liver injury as assessed by laboratory test values (“Hy’s Law Cases”) are also reportable as an SAE. If a Study subject develops abnormal values (3 x ULN) in aspartate transaminase (AST) or alanine transaminase

or both, concurrent with abnormal elevations (2 x ULN) in total bilirubin and no other known cause of liver injury, that event would be classified as a Hy's Law Case and an SAE.

Serious also includes any other event that the Investigator or sponsor judges to be serious, or which is defined as serious by the HRA in the country in which the event occurred.

Progression of the malignancy under study (including signs and symptoms of progression) should not be reported as SAEs unless the outcome is fatal during the trial or within the safety reporting period. Hospitalizations due to signs and symptoms of disease progression should not be reported as SAEs. If the malignancy has a fatal outcome during the trial or within the safety reporting period, then the event leading to death must be recorded as an adverse event and as an SAE with CTC grade 5.

The onset date of an SAE is defined as the date on which the event initially met serious criteria (e.g., the date of admission to a hospital). The end date is the date on which the event no longer met serious criteria (e.g., the date the patient was discharged from a hospital).

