8.3.5. Grading of Adverse Event Severity

To report adverse events on the CRFs, the Investigator will use the severity grading as described in NCI CTCAE (Version 4.0).

Every effort should be made by the Investigator to assess the adverse event according to CTCAE criteria. If the Investigator is unable to assess severity because the term is not described in NCI (Version 4.0), severity of MILD, MODERATE, SEVERE, LIFE-THREATENING, or FATAL may be used to describe the maximum intensity of the adverse event. For purposes of consistency, these intensity grades are defined as follows:

Table 21: Adverse Event Grading

Grade	Non-CTCAE Severity	Definition
1	Mild	Does not interfere with patient's usual function
2	Moderate	Interferes to some extent with patient's usual function
3	Severe	Interferes significantly with patient's usual function
4	Life-Threatening	Results in immediate risk of patient's death
5	Fatal	Results in patient's death

Note the distinction between the severity and the seriousness of an adverse event. A severe event is not necessarily a serious event. For example, a headache may be severe (interferes significantly with patient's usual function) but would not be classified as serious unless it met one of the criteria for serious events.

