Nonhematologic	Grade 3 or 4 nonhematologic toxicity with the following exceptions: 
 • Nausea, vomiting or diarrhea for < 48 hours^a • Asymptomatic electrolyte abnormalities that are corrected to grade 1 or better in < 48 hours^b

^aPatients with related grade 3 or 4 diarrhea, nausea or vomiting for ≥ 48 hours despite optimal medical therapy will require a one-level dose-reduction of TRC105.

^bPatients with related grade 3 or 4 electrolyte abnormalities that persist for ≥ 48 hours will require a one-level dose-reduction of TRC105.

Up to 15 patients with advanced renal cell carcinoma will be treated at the weekly dosing MTD (or top dose level if a MTD is not determined) to further characterize safety and tolerability. At

least 6 patients with advanced renal cell carcinoma will be treated at the every two week dosing MTD (or top dose level if a MTD is not determined).

Dose escalation will be according to the following dose escalation schema, based on the occurrence of DLT.

- If none of three patients in a cohort experiences a DLT after completing Cycle 1, dose escalation may be authorized by the medical monitor or designee.
- If one of three patients in a cohort experiences a DLT, three additional patients will be enrolled at the same dose level. If no additional DLT is reported, dose escalation may be authorized by the medical monitor or designee.
- If more than one of three or more than one of six patients at a dose level develop a DLT, the maximum tolerated dose (MTD) will be considered exceeded. Patient enrolment and treatment at that dose level will be stopped. There will be no further dose escalation and the previous lower dose will be designated as the MTD.
- Patients, who discontinue the study prior to completing the 28 day DLT evaluation period (Cycle 1), for reasons other than a DLT, will be replaced.

3.2. Phase 2

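### The Phase 1b DLT table leaves out isolated grade 4 thrombocytopenia and any nonhematologic event first recorded at grade 5

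*Protocol*

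**What the plan says.** Protocol Section 4.1.1.1 makes the DLT table a closed list: "DLT will have occurred when a patient has 1 or more toxicity listed in the table below", provided the toxicity is at least possibly related to the combination and falls in the 28-day window. Nothing elsewhere in the protocol or SAP adds death, grade 5 or investigator judgement to that list.

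The thrombocytopenia row reads "Grade > 4 thrombocytopenia or grade ≥ 3 thrombocytopenia and grade ≥ 3 hemorrhage", so the limit for thrombocytopenia alone is "Grade > 4 thrombocytopenia". The nonhematologic row reads "Grade 3 or 4 nonhematologic toxicity with the following exceptions"; the exceptions concern short-lived gastrointestinal events and corrected electrolyte abnormalities. Other rows have no upper limit, for example "Neutropenic infection: grade ≥ 3 neutropenia with grade ≥ 3 infection", and anemia counts from grade 3 upward. The Synopsis and SAP Section 3.1 carry the same limits.

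The protocol grades by CTCAE version 4.0 and uses grade 5 for a fatal outcome. Under Section 8.2.2, the event leading to a death from the malignancy "must be recorded as an adverse event and as an SAE with CTC grade 5".

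Patients who leave early without a DLT are replaced. The SAP says that those who stop before the end of the window "for reasons other than a DLT, will be replaced". Section 4.1.1.1 says much the same twice, but it also treats as evaluable a patient without DLT whose dose was reduced by documented toxicity.

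**The concern.** The Phase 1b primary objective is safety and the choice of a Phase 2 dose, and the DLT count is the quantity that drives escalation. If the table omits the most severe form of a toxicity, that event scores as no DLT however serious it is, and the 3+3 rule proceeds as if it had not occurred.

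This still matters because Phase 1b is unfinished. Section 2.3.4 reports 18 patients treated on the weekly schedule. Cohorts 3 and 4 and Expanded Cohort 2 remain, and Section 4.1.2.2 lets their result settle whether Phase 2 patients may move to 15 or 20 mg/kg every two weeks.

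**Working it through.** **Step 1: compare each limit with grades 3 to 5.**

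| Table 6 row | Limit | Counted | Not counted |
|---|---|---|---|
| Anemia | 3 or above | 3, 4, 5 | none |
| Neutropenic infection | 3 or above, both components | 3, 4, 5 | none |
| Thrombocytopenia with hemorrhage of grade 3 or above | 3 or above | 3, 4, 5 | none |
| Thrombocytopenia alone | above 4 | 5 | 3, 4 |
| Nonhematologic, outside the exceptions | 3 or 4 | 3, 4 | 5 |

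If the thrombocytopenia row is instead read so that hemorrhage qualifies both halves, isolated grade 4 is still not counted.

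**Step 2: narrow the nonhematologic gap.** Section 8.3.9 records every change of grade as a new adverse event. A related toxicity that passed through grade 3 or 4 in the window before becoming fatal therefore has its own listed record and is already a DLT, unless an exception applies. What escapes is an event first recorded at grade 5. The thrombocytopenia gap is not narrowed in this way.

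**Step 3: follow the uncounted patient.** A patient who dies of an unlisted related event could be replaced, under the replacement sentences in Section 4.1.1.1 and SAP Section 3.1. The same patient could be kept as evaluable without DLT, under the reduced-dose sentence in Section 4.1.1.1. The documents do not settle which. The sentences also differ on timing. Section 4.1.1.1 places evaluability in Cycle 2 for cohorts 3 and 4, whereas Section 10.3 and the SAP replacement bullet name Cycle 1. On either route the event adds nothing to the DLT count.

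**Step 4: effect in one cohort of three.**
- Event counted: 1/3, so three more patients are enrolled.
- Event uncounted, patient kept: 0/3, so escalation may proceed.
- Event uncounted, patient replaced: 0/2 with a third patient awaited; if that patient has no DLT, 0/3.

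This step needs no assumed rate.

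**Step 5: the plan's own figure, then an illustration.** Table 22 follows from P(escalate) = (1−p)³ + 3p(1−p)²·(1−p)³. At p = 0.10, 0.20 and 0.30 this gives 0.906, 0.709 and 0.494, against the stated 0.91, 0.71 and 0.49. All ten entries reproduce.

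The documents give no rate u of unlisted events, so the following values of u are assumptions. With a true rate of 30%, the rate the rule acts on is 0.30−u if such patients are kept, and (0.30−u)/(1−u) if they are replaced.

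| Assumed u | Kept: rate, P(escalate) | Replaced: rate, P(escalate) |
|---|---|---|
| 0 | 0.300, 0.49 | 0.300, 0.49 |
| 0.10 | 0.200, 0.71 | 0.222, 0.66 |
| 0.20 | 0.100, 0.91 | 0.125, 0.86 |

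These rows show the direction of the effect only. They do not estimate its size in this trial.

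**The case against.** **It is a drafting or conversion slip.** A lost symbol is unlikely: the greater-or-equal sign is read correctly twice in the same row, and the bare greater-than sign recurs in all three copies. A drafting slip is quite possible, but the text still governs scoring until it is changed. The nonhematologic gap does not depend on a symbol.

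**The omitted events are rare.** This largely stands. Table 4 (50 patients) lists no related thrombocytopenia and no grade 5 event. Section 2.3.2.1 reports no suspected grade 4 or 5 events with bevacizumab. Section 2.3.4.1 mentions neither thrombocytopenia nor death in this trial. Section 2.3.6.1 does report a grade 5 intracranial hemorrhage with TRC105 and bevacizumab, but in a glioblastoma patient with markedly abnormal clotting, and it does not state relatedness.

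**Someone would notice.** Escalation follows a safety review with the principal investigators (Section 4.1.1.1), and the SAP says only that the medical monitor may authorize it. The recommended dose follows review of the whole toxicity profile. These safeguards would probably catch a death. They are discretionary, though, and leave the DLT count unchanged.

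**Stronger readings.** A reader might infer that every fatal related toxicity falls outside the definition and that the patient is simply replaced. The documents do not support this: the open-ended hematologic rows include grade 5, fatal thrombocytopenia meets the stand-alone limit, Section 8.3.9 captures events that passed through grade 3 or 4, and replacement is ambiguous. A reader might also take 0.71 or 0.91 as the real chance of escalating at a 30% DLT rate. Those figures need 10 or 20 percentage points of unlisted events, which nothing in the documents supports.

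**Conclusion.** The point holds in a limited form. As written, isolated grade 4 thrombocytopenia is never a DLT, and neither is a related nonhematologic event first recorded at grade 5. Both follow from the closed-list sentence and the five-grade scale, and the nonhematologic limit is also inconsistent with other rows of the same table. The reach is the cohorts still to be scored: 3, 4 and Expanded Cohort 2. The effect is at most one DLT removed from the count per such event, which in a cohort of three is enough to change the decision. Its frequency is unknown and probably low, so no change in escalation probability should be claimed. The point is worth settling because it touches the decision rule for the Phase 1b primary objective and can be corrected at little cost.

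**What to change.** Before cohorts 3 and 4 are scored, the sponsor should:
- reconcile the thrombocytopenia and nonhematologic grade limits in the Synopsis, Protocol Table 6 and SAP Section 3.1 with the CTCAE grades 1 to 5 and with the open-ended rows of the same table. Table 21, where grade 5 is "Results in patient's death", is a fallback for terms not described in CTCAE, so Section 8.2.2 is the better reference for grade 5;
- reconcile the replacement and evaluability sentences in Protocol Sections 4.1.1.1 and 10.3, the Synopsis and SAP Section 3.1, so that the handling of a patient who dies of related toxicity in the window is unambiguous, including which cycle applies to cohorts 3 and 4.

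The sponsor's clinicians choose the limits; no particular limit is proposed here. The cost is wording in two documents and, depending on the limits chosen, a slightly lower chance of escalation.
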